### 15.44 Administration

Tiragolumab is delivered through an IV administration set with a 0.2-micron inline filter over 60 minutes. Tiragolumab must not be infused into the same line or cannula concomitantly with other drug infusions, including parenteral nutrition. Infusions of blood products and any electrolyte supplementation must not occur simultaneously with infusions of tiragolumab.

If the first infusion is tolerated without infusion-associated adverse effects, the second infusion may be delivered over 30 (±10) minutes. If the 30-minute

infusion is well tolerated, all subsequent infusions may be delivered over 30 ( $\pm 10$ ) minutes.

15.45 Pharmacokinetic information

**Elimination half-life:** Elimination half-life is approximately 15 days

15.46 Potential drug interactions

No specific drug interaction studies have been performed with tiragolumab

15.47 Known potential adverse events

Infusion-related reactions (IRRs) are well recognized side effects of monoclonal antibody infusions. The incidence and severity of IRRs vary according to the target antigen. Based on clinical trial experience with single-agent tiragolumab, acute IRRs were experienced in 11.9% of patients. Serious IRRs were not reported. Most of IRRs were with Grade 1 and 2 symptoms, such as pyrexia (fever), chills, hypertension, and nausea. Based on clinical trial experience with tiragolumab combined with atezolizumab in a phase 1b and a phase II study, IRRs were experienced in 10.0% and 28.4% of patients, respectively. All IRRs in the combination studies that were related to tiragolumab were Grade 1 and 2, and considered non-serious. Pyrexia was the most commonly reported symptom, but pruritus, anxiety, chills, dyspnea, joint stiffness, rash, temperature intolerance, and wheeze were also reported.

15.48 Drug procurement

Tiragolumab is supplied by Genentech, Inc., to each site for study use.

15.49 Nursing Guidelines:

15.491 Infusion should occur over 60 minutes (first infusion) with a 0.2-micron inline filter. Do not infuse tiragolumab with other drug infusions.

If well-tolerated, subsequent infusions may be over 30  $\pm 10$  minutes.

15.492 Approximately 11% of patients experienced infusion related reactions, mostly Grade 1 or 2. Symptoms included pyrexia, chills, hypertension, and nausea.

15.493 Pyrexia was the most commonly reported symptom.

15.494 Patients can experience rash and pruritis.

15.495 Shortness of breath and wheezing have been reported.

## 16.0 Statistical Considerations and Methodology

### 16.1 Study Design and analysis plan

#### 16.11 Neoadjuvant Phase (Pre-surgery)

##### 16.111 Primary Endpoint

##### 16.1111 Arms A and B

The primary objective of the neoadjuvant portion of this trial is to obtain an point and interval estimate of pathologic complete response rate in patients with Stage III BRAFm melanoma after 12 weeks of neoadjuvant vemurafenib/ cobimetinib/ atezolizumab therapy as well as point and interval estimate of pathologic complete response rate in patients with Stage III BRAFwt melanoma after 12 weeks of neoadjuvant atezolizumab therapy.

Pathologic complete response (ypCR) rate defined as the percentage of patients with no residual disease found in the surgical specimen among the patients who began neoadjuvant protocol treatment.

For each patient cohort, estimate of pCR to neoadjuvant treatment rate is calculated as follows: 100% times the number of patients who have no residual disease found on pathologic evaluation of the surgery specimen among the patients who started protocol treatment. An interval estimate will be obtained using the formula for a 90% binomial confidence interval for one sample proportion.

With a sample size of 15 patients per patient cohort, the 90% binomial confidence interval for ypCR rate is given below for a number of possible outcomes.

number of patients with no residual disease found in surgical specimen	ypCR (90% confidence interval for the ypCR rate)
1	6.7% (0.32-27.9%)
4	26.7% (9.7-51.1%)
5	33.3 (14.2-57.7)%
7	46.7% (24.4-70.0)%
10	66.7% (42.2-86.8%)
13	86.7 (63.66-97.6%)
15	100% (81.9-100%)

16.12 Adjuvant Phase (Post-surgery)

The primary endpoint is the median recurrence-free (RFS) rate. Recurrence-free survival is defined as the time from surgery to radiographic or histologic evidence of local, regional, or distant recurrence of melanoma or death due to any cause

All patients who began adjuvant treatment will be included in the analysis of RFS. Those without evidence of disease recurrence will be censored at the time of their last disease evaluation. For each regimen, the distribution of recurrence-free survival times [denoted as  $RFS(t)$ ] will be estimated using the Kaplan-Meier method. A 90% confidence interval for  $V(t) = \log [-\log (RFS(t))]$  will be constructed and then the inverse transformation  $\exp[-\exp v(t)]$  will be used to obtain a confidence for  $RFS(t)$ . We will estimate RFS for all patients and separately for BRAF-mutated and BRAF-wild-type patients.

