#### 2.12 Adjuvant phase primary objectives

- 2.121 To assess recurrence-free survival (RFS) in patients with stage III BRAFm melanoma after neoadjuvant vemurafenib/cobimetinib/atezolizumab, surgery, and adjuvant atezolizumab.
- 2.122 To assess RFS in patients with stage III BRAFwt melanoma after neoadjuvant cobimetinib/atezolizumab, surgery, and adjuvant atezolizumab.
- 2.123 To assess RFS in patients with stage III melanoma after neoadjuvant atezolizumab/tiragolumab, surgery, and adjuvant atezolizumab.

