### 13.2 Surgery

Patients who were not rendered NED will go to the survival follow-up (event monitoring) phase of the study where progression and survival information will be collected every 6 months for a maximum of 5 years post-registration. Subsequent treatment is at the discretion of the patient's medical team.

Patients who are rendered NED but refuse to begin the protocol-specific adjuvant treatment will go survival follow-up (event monitoring) phase of the study where progression and survival information will be collected every 3 months until disease progression and then every 6 months for a maximum of 5 years post-registration. Subsequent treatment is at the discretion of the patient's medical team

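### RFS is timed from surgery but analysed only in patients who began adjuvant treatment, so recurrences and deaths before that start drop out and the adjuvant-phase primary estimate is biased upward

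*Combined protocol and SAP*

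**What the plan says.** Section 16.12 sets the adjuvant-phase primary endpoint: "The primary endpoint is the median recurrence-free (RFS) rate". It fixes the time origin: "Recurrence-free survival is defined as the time from surgery to radiographic or histologic evidence of local, regional, or distant recurrence of melanoma or death", from any cause. It then fixes the analysis set: "All patients who began adjuvant treatment will be included in the analysis of RFS". Censoring is conventional: "Those without evidence of disease recurrence will be censored at the time of their last disease evaluation". The estimator is Kaplan-Meier with a 90% log-minus-log interval. No delayed entry, landmark or sensitivity analysis in all resected patients is described there or elsewhere.

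The matching Arm C objective in Section 2.12 reads: "To assess RFS in patients with stage III melanoma after neoadjuvant atezolizumab/tiragolumab, surgery, and adjuvant atezolizumab".

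Section 7.3 reserves adjuvant treatment for completely resected patients. Section 13.2 covers one group who do not start it: "Patients who are rendered NED but refuse to begin the protocol-specific adjuvant treatment will go survival follow-up (event monitoring) phase". They are contacted every 3 months until progression and every 6 months after that. Section 16.131, written for Arms A and B, follows everyone who completes surgery to progression or 5 years from registration.

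On timing, the schemas give about 4 to 6 weeks for surgery, and Section 7.2 places the operation 2 to 4 weeks after neoadjuvant treatment ends. No upper limit is given for the interval from surgery to first adjuvant dose. The schedules in Sections 4.1 and 4.2 show a history and examination within 7 days before adjuvant start, but no imaging between surgery and that start.

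**The concern.** Entry to the analysis depends on something that happens after time zero. A patient who recurs or dies between surgery and the first adjuvant dose has had an RFS event by the plan's own definition but never enters the denominator. Those who do enter carry a stretch of follow-up in which, by construction, no event could occur. Kaplan-Meier from surgery treats that stretch as observed risk time.

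This affects the primary endpoint of the adjuvant phase in all three arms. The RFS-based correlative analyses in Sections 16.21 and 16.22 use the same outcome and name no other population. The confidence interval does not reflect the error, because it describes sampling variation only.

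**Working it through.** The plan gives no RFS target, event count or precision figure, so there is nothing of its own to reproduce. What follows is an illustration under stated assumptions.

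**Inputs.**
- Hazard: constant. The starting median is 15.4 months, which Section 1.2 gives for adjuvant ipilimumab in macroscopic nodal disease. It is used only as a plausible hazard; 30 and 60 months are added as assumptions.
- Gap g from surgery to adjuvant start: 4 to 6 weeks, reading the schema figure as the post-operative interval, with 2 and 12 weeks as alternatives.
- Resected patients: 28, assumed, from the 32 who start treatment in Arm C.

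**Formula.** With hazard λ = ln 2 / median, S(t) = exp(−λt). Restricting to patients event-free at g while timing from surgery estimates S(t)/S(g), and the median becomes g + median.

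**Numbers at a 15.4-month median.** λ = 0.693/15.4 = 0.0450 per month, and S(12) = 58.3%.
- 4 weeks (0.92 months): S(g) = 0.959. As written, 12-month RFS is 60.7% and the median 16.3 months.
- 6 weeks (1.38 months): S(g) = 0.940. As written, 12-month RFS is 62.0% and the median 16.8 months.
- Expected early events lost from 28 patients: 28 × 0.041 = 1.1 and 28 × 0.060 = 1.7.

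**Inflation of 12-month RFS, in points (differences taken before rounding):**

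| Median RFS | 2 wk | 4 wk | 6 wk | 12 wk |
|---|---|---|---|---|
| 15.4 months | 1.2 | 2.5 | 3.7 | 7.7 |
| 30 months | 0.8 | 1.6 | 2.5 | 5.0 |
| 60 months | 0.5 | 0.9 | 1.4 | 2.8 |

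The median shifts by g itself: 0.5, 0.9, 1.4 and 2.8 months.

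**Simulation.** Over 4,000 runs with 28 resected patients, a 15.4-month median and gaps uniform on 4 to 6 weeks, mean 12-month RFS was 58.0% for all resected patients from surgery, 61.2% as written, and 58.1% for starters timed from adjuvant start. The last agrees with the first because the hazard is constant. With a changing hazard it would answer a slightly different question, but without guaranteed event-free time.

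**By counts.** If true 12-month RFS is 60%, dropping one early event gives 0.60 × 28/27 = 62.2% for 28 resected, or 0.60 × 15/14 = 64.3% for 15, the planned size of Arm A or B if all were resected.

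**Event-free non-starters.** Let 10 to 20% of resected patients not start while still event-free, with a 15.4-month median in starters. Leaving them out changes 12-month RFS by nothing if their hazard equals that of starters, by +2.4 to +4.9 points if it is double, and by −1.8 to −3.6 points if it is half.

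**The case against.** **The effect is modest.** The schedules count the pre-operative visit within the surgical period. If the 4 to 6 weeks run from the end of neoadjuvant treatment, and 2 to 4 of them precede surgery, only about 0 to 4 weeks remain afterwards. With no scan due before adjuvant start, only deaths and clinically evident recurrences would be removed; occult ones would surface later among starters and be counted. The approximate 90% half-width at 60% RFS, ignoring censoring, is 1.645 × √(0.6 × 0.4/28) = 15 points, or 21 points with n = 15. All of this stands as to size. It does not remove the mismatch.

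**The objective concerns patients who receive all three components.** That can justify a starter population, but not a clock that begins before a patient can qualify. The closing sentence of Section 16.12, which promises estimates for all patients and by BRAF status, separates the overall estimate from the subgroups; it does not widen the set.

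**Stronger readings that the documents do not support.**
- A reader might infer that every exclusion before adjuvant start flatters the result. For event-free refusals or unfit patients that is not established, as the last calculation shows. If enough of them had a better prognosis, their omission could offset the guaranteed-time effect.
- A reader might infer a bias near 9 points. Four early events among 28, with 65% RFS in starters, give 0.65 × 24/28 = 56%. At the 15.4-month median, losing four of 28 needs a gap of about 15 weeks.
- A reader might set RFS against all treated patients: 0.65 × 27/32 = 55% down to 0.65 × 24/32 = 49%, a difference of 10 to 16 points. That compares two estimands. Patients never rendered disease-free have no recurrence-free interval. Failures before surgery count against the pCR endpoint, whose denominator is everyone who started neoadjuvant treatment, and unresectable progression has its own stopping rule in Section 16.321.
- A reader might fear a wrong trial decision. RFS here is estimation only, with no hypothesis, threshold or planned external comparison.

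**Conclusion.** The point holds. As written, Section 16.12 excludes recurrences and deaths between surgery and first adjuvant dose and credits the remaining patients with guaranteed event-free time, which biases the primary RFS estimate upward. The direction is certain for those events only.

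Under exponential RFS with a 4 to 6 week gap, the inflation at 12 months is about 2.5 to 3.7 points at a 15.4-month median and about 1 to 1.4 points at 60 months. It could be near 1 point if the gap is 2 weeks, or near 8 points if starts slip to 12 weeks, both at the 15.4-month median. The hazard and the gap are assumptions. The absence of a pre-adjuvant scan would lower these figures, and the absence of a maximum gap leaves the upper end open. The effect is small beside sampling error, but it is systematic and avoidable.

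**What to change.** Amend Section 16.12 so that clock and population agree, by one of two routes.

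1. Analyse all patients completely resected (NED) at surgery, timed from surgery, whether or not adjuvant treatment starts.
2. Keep the adjuvant starters and time RFS from the first adjuvant dose. Delayed entry at that date, with time still measured from surgery, is an alternative. Its early risk sets will be small, and the curve is conditional on being event-free at the earliest start.

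Under either route, report how many resected patients did not start, with reasons, and name the same set for the RFS correlatives.

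Route 2 needs no new data. Route 1 uses follow-up already collected under Sections 4.3, 13.2 and 16.131, with two costs. Non-starters are followed in event monitoring, whose schedule lists no imaging, whereas Section 11.3 gives starters PET/CT every 12 weeks, so recurrences are ascertained differently. Section 13.2 also mentions only patients not rendered NED and those who refuse; a sentence should state the follow-up of NED patients who recur or become unfit before adjuvant start. The estimate is likely to be slightly less favourable.

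Event-free survival from first neoadjuvant dose in all treated patients is an optional supplement. It answers a different question and is not needed to correct this one.

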#### 16.13 Study Duration

##### 16.131 Arms A and B

It is anticipated that the accrual period will be 15-18 months. All patients who complete surgery will be followed until disease progression or a maximum of 5 years after registration. Thus, study duration will be appropriately 5.5 years from opening (enrollment period 15-18 months; neoadjuvant treatment and surgical period after close of enrollment for last patient enrollment being approximately 3 months, then adjuvant treatment and follow-up period after last patient completes surgery being 3 years, and then data analysis and manuscript preparation being approximately 6 months).

##### 16.132 Arm C

We anticipate enrollment of 1 patient per month for this arm. An additional 4 patients may be necessary to replace patients refusing to initiate study treatment. That is, maximum enrollment may reach 36 patients (estimated 36-month enrollment period). (At the present rate of enrollment at Mayo Clinic and University of Minnesota, the enrollment period would be approximately 36 months.)

#### 16.2 Correlative endpoints

##### 16.21 Pretreatment sPD-L1, pretreatment tumor PD-L1, and pretreatment intracellular Bim in tumor-related T cells

To gather preliminary data as to whether the RFS of patients with stage III melanoma receiving neoadjuvant vem/cobi/atezo or atezo, followed by surgery and adjuvant atezo differs with respect to either pretreatment sPD-L1 or pretreatment intracellular Bim in tumor-related T cells, stratified Cox modeling will be conducted with patient cohort as the strata to obtain a point and interval estimate of the hazard of recurrence among those with biomarker levels thought to be delirious relative to the hazard of recurrence among those with biomarker levels thought not to be delirious.

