##### 1.42 *Clinical data supporting the use of neoadjuvant therapy*

While the many potential advantages of neoadjuvant therapy are described above, some have expressed concern that neoadjuvant therapy might actually be harmful for some patients. If neoadjuvant therapy were ineffective at regional control, then delaying surgery might convert initially resectable disease to unresectable disease. To address this concern in our proposed patient cohort, we retrospectively evaluated a series of high-risk stage III melanoma patients treated at Mayo Clinic between 2009 and 2016 with a variety of neoadjuvant therapies. Of the patients analyzed, only 6% (1/16) of patients with initially resectable or borderline-resectable disease progressed to regionally unresectable disease after neoadjuvant therapy, whereas 63% (5/8) patients with initially unresectable disease responded regionally such that disease became resectable [unpublished data]. Further, as discussed above in Section 1.3, the safety of neoadjuvant systemic therapy for multiple other epithelial cancers has been well-established. It seems logical then that with the advent of effective therapies for melanoma in the metastatic setting moving systemic therapy in part to the neoadjuvant setting for patients who are identified at the time of diagnosis as suitable candidates for systemic therapy would be as safe as and potentially more efficacious than postoperative adjuvant therapy.

In addition, there are now five open single institution phase I or II clinical trials testing neoadjuvant therapy for melanoma patients (Clinicaltrials.gov 2017). Three trials are evaluating immunotherapy. NCT01608594, a phase I trial of Stage III  $\geq$  N1b patients testing ipilimumab 10 mg plus high dose interferon $\alpha$ 2b versus ipilimumab 3 mg plus high dose interferon $\alpha$ 2b followed by low dose interferon $\alpha$ 2b for 46 weeks postoperatively with the primary aim of safety and secondary

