## 4.3 Event Monitoring/Survival Follow-up

	Event Monitoring Phase 				
	q. 3 months until PD	At PD	After PD q. 6 months	Death	New Primary
Event Monitoring	X	X	X	X	At each occurrence

1. If a patient is still alive 5 years after registration, no further follow-up is required.

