12.2 Location: 1 nodal basin vs. >1 nodal basin

12.3 Baseline tissue PD-L1 staining: None versus low versus high

12.4 BRAF mutation status: wild type or mutated

## **13.0 Treatment/Follow-up Decision at Evaluation of Patient**

### **13.1 Neoadjuvant phase**

13.11 Patients who have not had progression of disease or intolerable toxicity may continue on study per protocol.

13.12 Patients who have not had disease progression but develop intolerable toxicity during neoadjuvant treatment may be eligible for retreatment at a lower dose ([Section 8.0](#)) or proceed to surgery.

13.13 Patients who progress during neoadjuvant treatment and are still surgical candidate may proceed to surgery.

13.14 Patients who progress during neoadjuvant treatment and are no longer a surgical candidate will complete on-study, neoadjuvant treatment, and end of protocol treatment form. Survival follow-up is required. Subsequent treatment is at the discretion of the patient's medical team.

13.15 Patients who are no longer a surgical candidate after discontinuation of neoadjuvant treatment for reasons other than disease progression will complete on-study, neoadjuvant treatment, and end of protocol treatment form. Survival follow-up is required. Subsequent treatment is at the discretion of the patient's medical team.

13.16 Patients who discontinue neoadjuvant treatment and are refusing all remaining protocol treatment (that is, surgery and adjuvant treatment) will complete on-

study, neoadjuvant treatment, and end of protocol treatment form. Survival follow-up is required. Subsequent treatment is at the discretion of the patient's medical team.

- 13.17 Patients who discontinue neoadjuvant treatment due to other medical conditions will complete on-study, neoadjuvant treatment, and end of protocol treatment form. Survival follow-up is required. Subsequent treatment is at the discretion of the patient's medical team.

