#### 14.4 Background and methodology

##### 14.41 Bim assays

The pro-apoptotic molecule Bim is upregulated in tumor-related T cells upon engagement of PD-1. We have demonstrated that high levels of Bim on pre-treatment tumor-related T cells (reflective of a high level of PD-1 engagement) are associated with clinical responses to anti-PD-1 (Dronca 2016).

Using our previously published flow cytometry technique (Dronca 2016), we will label cells with CD8, CD11b, PD-1, and intracellular Bim. Tumor-related T cells will be defined as CD8+11b+PD-1+. We will determine the frequency of Bim+ tumor-related T cells both prior to treatment and after neoadjuvant therapy, as well as before and after adjuvant therapy. We will correlate baseline and changes in Bim with RFS and pCR.

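### The only time-to-event analysis of pretreatment sPD-L1, tumor PD-L1 and Bim uses RFS from surgery in patients who began adjuvant treatment; event-free survival from first dose should be added.

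*Combined protocol and SAP*

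**What the plan says.** Section 16.21 covers pretreatment sPD-L1, tumor PD-L1 and intracellular Bim in its title; its text names sPD-L1 and Bim. The method is that "stratified Cox modeling will be conducted with patient cohort as the strata to obtain a point and interval estimate of the hazard of recurrence" in patients with unfavourable marker levels relative to the others. The purpose is to gather preliminary data. Section 16.22 plans the same correlative work for Arm C, including soluble and tissue PD-L1 and Bim against RFS.

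Section 16.21 gives no endpoint definition or analysis set of its own, so section 16.12 governs: "Recurrence-free survival is defined as the time from surgery to radiographic or histologic evidence of local, regional, or distant recurrence of melanoma", or death, and "All patients who began adjuvant treatment will be included in the analysis of RFS".

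Several groups never reach that set:
- Section 13.14, which begins "Patients who progress during neoadjuvant treatment and are no longer a surgical candidate will complete on-study", ends protocol treatment for these patients but requires survival follow-up.
- Sections 13.15 to 13.17 do the same for patients not resected for other reasons.
- Section 13.2 sends two further groups to event monitoring: patients not rendered disease-free at surgery, and patients rendered disease-free who decline adjuvant treatment.

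Section 4.3 schedules event monitoring "q. 3 months until PD" and 6-monthly afterwards, up to 5 years from registration. Section 16 defines no event-free, progression-free or overall survival analysis from registration or first dose.

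The markers are also related to pCR. For Bim, section 14.41 says "We will correlate baseline and changes in Bim with RFS and pCR". Section 14.42 does the same for sPD-L1, and objective 2.34 for tumor PD-L1.

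**The concern.** The markers are measured before the first dose, but their time-to-event outcome begins months later. It exists only for patients who stayed resectable, had surgery, were completely resected and started adjuvant atezolizumab. Each step comes after baseline and may depend on the marker. Conditioning on them removes the earliest treatment failures from the one analysis that uses timing.

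Two things are at stake. A marker whose effect is concentrated before surgery would look null in the RFS model. And even a marker with the same effect throughout would be assessed on fewer events, in a pilot with few to spare. Progression to unresectability is serious enough to close an arm permanently under section 16.321, yet it is not an event in any time-to-event analysis.

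**Working it through.** **Inputs from the documents**
- Treated patients: 30 in Arms A and B (schema) plus 32 in Arm C (16.1112) = 62.
- Loss before surgery: section 1.42 reports that "only 6% (1/16) of patients with initially resectable or borderline-resectable disease progressed to regionally unresectable disease". 1/16 = 6.25%, which reproduces the printed 6%; the exact 90% interval is 0.3% to 26.4%. This counts regional unresectability only, so it is probably a low anchor.
- Upper reference: 30%, the closure limit in 16.321. It is a boundary, not an expected rate.
- Recurrence after surgery: 2 of 18 on immunotherapy at 10 months' median follow-up (1.42). Section 1.2 gives a less favourable anchor, a median of 15.4 months on adjuvant ipilimumab.

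**Assumptions**: 15% as a middle loss rate; exponential times; surgery at month 4; 36 months' follow-up from first dose, so 32 months after surgery; every resected patient starts adjuvant treatment. Treating 2/18 as a 10-month risk is itself an approximation.

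**Step 1: patients lost before surgery.** 62 × 0.0625 = 3.9; 62 × 0.15 = 9.3; 62 × 0.30 = 18.6.

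**Step 2: events available.** Hazard = −ln(16/18)/10 = 0.0118 per month. Risk over 32 months = 1 − exp(−0.0118 × 32) = 0.314. RFS events = 62 × (1 − loss) × 0.314. Event-free survival (EFS) events = RFS events + patients lost.

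| Loss before surgery | RFS events | EFS events |
|---|---|---|
| 6.25% | 58.1 × 0.314 = 18.3 | 22.1 |
| 15% | 52.7 × 0.314 = 16.5 | 25.8 |
| 30% | 43.4 × 0.314 = 13.6 | 32.2 |

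A simulation on the same set-up, with a continuous marker, gave mean event counts of 18.5 v 22.3 at 6% and 16.4 v 25.6 at 15%.

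Using the 15.4-month median instead, with 36 months after surgery: hazard = ln 2/15.4 = 0.0450 and risk = 1 − exp(−0.0450 × 36) = 0.802. At 6.25% loss this gives 58.1 × 0.802 = 46.6 RFS events against 50.5 EFS events. The same 3.9 events are recovered, but they matter less.

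**Step 3: what that means for power.** For a marker splitting patients evenly with a constant hazard ratio of 2 (both assumed), power at two-sided 10% is Φ(√(D/4) × ln 2 − 1.645). With D = 18.3 it is 43%; with D = 22.1 it is 49%. With D = 46.6 and 50.5 it is 76% and 79%.

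**Step 4: the estimate itself.** Large-sample simulation (400,000 patients, half marker-positive, surgery at 3.5 months, 36 months after surgery, 15.4-month median) gave these results for a marker that acts only before surgery:

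| Loss before surgery | RFS HR | EFS HR, early relative risk 3 | EFS HR, early relative risk 5 |
|---|---|---|---|
| 6.25% | 1.00 | 1.08 | 1.11 |
| 15% | 1.00–1.01 | 1.22 | 1.30 |
| 30% | 1.00–1.01 | 1.52 | 1.77 |

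With a constant hazard ratio of 2 and no frailty, both analyses return 2.0. With gamma frailty of variance 1 or 2, RFS returns 1.47 or 1.32 and EFS 1.57 or 1.44.

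**The case against.** A reader might infer that patients who fail early enter no marker analysis at all, or surface only in the closure rule. The documents do not support that. Bim, sPD-L1 and tumor PD-L1 are each also related to pCR, and the pCR rate is taken over everyone who started neoadjuvant treatment (16.1111, 16.1112). On that denominator a patient who never reaches surgery counts as non-pCR. This stands, but the cover is partial. Non-pCR merges unresectable progression with ordinary residual disease and ignores timing. Section 16.21 gives no pCR method for these markers. Section 14.42 speaks of response at surgery, which leaves patients without surgery unclear.

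The second objection is that RFS is the outcome the objectives name (2.31, 2.32, 2.34), the work is exploratory, and a constant hazard ratio gives no attenuation. All of that is right. It makes EFS an addition rather than a replacement and limits the importance of the point. At 6% loss the gain for an early-only marker is slight (EFS hazard ratio 1.08 to 1.11).

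Third, EFS brings its own difficulty. The Arm C schedule has no routine imaging between baseline and the end of neoadjuvant treatment, so progression dates before surgery will cluster at that scan.

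**Conclusion.** The point holds as a gap in the time-to-event analysis. The only such model for these baseline markers is fitted in a set selected on later success, and no analysis from first dose is defined although progression and survival are followed.

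It does not follow that the RFS hazard ratio is generally attenuated. It is near 1.0 if the marker acts only before surgery, somewhat lower than the EFS estimate under frailty, and unbiased under a constant hazard ratio without frailty, where the cost is events and power. On the protocol's own 1/16 and 2/18, about 4 of 22 events are lost. The number rises with the loss rate, and its importance falls if recurrence is more frequent. Apart from those two proportions, the patient numbers and the 15.4-month median, the sizes rest on assumed loss rates, hazard ratios, marker prevalence and frailty. Because the analysis is exploratory, this is a cheap improvement and not a threat to the trial's primary results.

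**What to change.** Add to section 16.21, for sPD-L1, tumor PD-L1 and Bim:
- **Endpoint:** event-free survival from first neoadjuvant dose, in all patients who start treatment.
- **Events:** progression precluding surgery, residual disease not rendered disease-free at surgery, recurrence, or death from any cause.
- **Other patients without surgery:** those unresected for toxicity, refusal or other illness stay in follow-up until progression or death, and are otherwise censored at last disease evaluation.
- **Method:** the same Cox model stratified by cohort, plus a Kaplan-Meier curve per arm with a 90% interval.

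Keep RFS from surgery as the analysis named in the objectives, and state that it describes patients who began adjuvant treatment.

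The cost is one definition, one extra model and one extra exploratory endpoint to report. No new visits or data are needed. The report should note that progression dates before surgery cluster at the end-of-neoadjuvant scan.
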